Tumor bed localisation and open or closed cavity BCS:With superficial closure, only the superficial aspect of the cavity is closed, allowing the formation of a seroma to prevent deformation of the breast. A full-thickness closure consists of repositioning of the surrounding breast tissue and suturing the deep and superficial layers, preventing the development of significant seroma. There is a paucity of data on the influence of surgical closure techniques on EB treatment planning. It can be hypothesized that superficial closure may lead to a better-delineated cavity as a well-visualized seroma has been shown to decrease interobserver variations nevertheless, it may also lead to a larger treatment volume and greater late toxicity effects. However, with full-thickness closure, the surgical clips may be displaced with the approximation of the surrounding breast tissue and not correlate with the true extend of the cavity. In a recently published single institutional experience, Shaikh et al.⁹ did not find statistically significant difference in mean cavity visualization scoring (CVS) (Smitt et al¹⁰, 1 = no visible cavity, 2–4 = heterogeneous cavity with indistinct, distinct, or clearly defined margins, 5 = homogenous cavity with clearly defined margins) or normal tissue dosimetric endpoints between 29 patients who underwent superficial closure and sixteen patients who underwent full-thickness closure. A higher percentage of patients who underwent superficial closure had CVS scores >2 (79% vs. 63%). The small patient numbers in each cohort and its retrospective nature are the limitations of the study.

Oncoplastic BCS techniques with parenchymal rearrangement present new challenges to the localisation of the tumour bed and therefore delivery of local boost radiotherapy. Although use of whole-breast radiation therapy (RT) is straightforward, difficulties in localization of the tumor bed for the local RT boost have not been investigated.

Pezner et al¹¹ carried out a retrospective review of 25 patients who received RT after breast conservation surgery with oncoplastic reconstruction. It was found that among 11 patients with a minimum of 4 surgical clips placed at tumor resection, 8 (73%) had the final tumor bed extend beyond the original breast quadrant or be completely relocated into a different

region. In 3 (27%) cases, the clinical treatment volume was 2 to 3 separated regions within the breast.

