The margins to be given to tumour bed for defining boost field have also been discussed. Harrington et al¹⁴ have shown that a boost field marked on the basis of clinical data and background with a margin of 2 cm all around covers radiological field with same margin in only 1/3rd (33%) of patients. Although Vicini et al. showed that a margin of 1 cm around the tumour covers microscopic disease adequately, in EORTC trial margins of 1.5 cm were given for microscopically completely excised tumours. Overall, a margin of 1.5-2 cm to the tumour bed has been reported to cover all subclinical disease in patients with clear microscopic margins.

Some institutions have practised tumour bed boost by 4-6 MV photons. The practice of delivering boost by photons has declined after widespread availability of electrons due to

higher penetration and increased doses to underlying critical structures. Photons can be used in patients with small tumour bed as late term sequelae of electrons such as telangiectasia may not be acceptable to some patients treated with electrons.

Aims and Objectives: Primary objective- To evaluate dosimetric outcomes in tumor bed boost irradiation in patients undergoing breast conservative surgery using three different surgical techniques

Secondary objective-Evaluation of cosmesis in patients prior to radiotherapy, at the time of completion of radiotherapy and 6 months post completion of radiotherapy

Material and methods-

Patients will be screened for the study at the time of radiotherapy simulation for External beam radiotherapy

The sample size has not been calculated as this is a pilot study. Twenty patients will be accrued for the purpose of this study. The patients will be divided into three groups:

Group A- Patients who underwent open cavity BCS

Group B- Patients who underwent closed cavity BCS

Group C- Patients who underwent oncoplasty

Inclusion Criteria- All patients undergoing Breast Conservative Surgery (Open Cavity/Closed Cavity) or Oncoplasty will be eligible for this study.

Exclusion Criteria-1. Patients undergoing Neoadjuvant chemotherapy will not be eligible for the purpose of this study.

2. All patients undergoing Modified Radical Mastectomy will not be eligible for the purpose of this study

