The following dosimetric variables will be determined for each patient -seroma cavity volume (ccs). PTV volume (ccs). In addition the ratio between the PTV volumes to the whole breast volume will be determined. The Radiation Conformity Index (RCI) will be determined for both set of plans. It was first defined by Knoos et al and a revised definition appeared in ICRU 62 It is the ratio of volume of the PTV to the volume that receives 95% prescribed dose or higher ($RCI = V_{PTV} / V_{95\%}$). The Dose Homogeneity Index (DHI) will be determined for both set of plans (DHI). It is ratio of dose received by 95% of PTV volume to the dose received by 5% of PTV volume ($DHI = D_{\geq 95\%(\text{within PTV})} / D_{\geq 5\%(\text{within PTV})}$). The dose received by several normal structures will be determined for both set of plans-normal ipsilateral breast tissue (Whole breast volume- PTV volume), contralateral breast, ipsilateral lung, contralateral lung and heart

The borders of the portal will be modified based on the position of the lumpectomy cavity/seroma of the scan and marked on the patient. The boost irradiation for all patients will be done using electrons. The energy of electrons required will be decided from the depth of the lumpectomy cavity.

In addition the cosmesis will be determined for all the patients prior to starting radiotherapy, at the time of conclusion of radiotherapy and 6 months post completion of radiotherapy. This will be done by using the criteria suggested by Harris et al

1. Excellent: the treated breast almost identical to the untreated one.
2. Good: the treated breast slightly different from the untreated breast.
3. Fair: obvious difference between the two sides without major distortion.
4. Poor: the treated breast is seriously distorted.

Statistical analysis shall be performed with the Statistical Package for Social Sciences (SPSS, Chicago, IL) software package, version 21.0, for Windows A two-tailed PValue less than 0.05 will be considered as statistical significance in this study. Descriptive statistics, including frequency distributions, means \pm SD, and 95% confidence intervals, to be calculated for demographic and treatment variables. The statistical analysis will be carried out using the One way ANOVA or Krsukal Wallis test and categorical comparison will be done using Chi Square test.

References:

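### No effect estimate or confidence interval is planned for any difference between surgical techniques; the comparison rests on a three-group omnibus p-value in 20 patients

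*Combined protocol and SAP*

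**What the plan says.** The primary objective (Aims and Objectives) is "To evaluate dosimetric outcomes in tumor bed boost irradiation in patients undergoing breast conservative surgery using three different surgical techniques". Under Material and methods, "Twenty patients will be accrued for the purpose of this study" and "The patients will be divided into three groups", defined by the operation received: open cavity, closed cavity or oncoplasty. No group sizes are given. On the number itself: "The sample size has not been calculated as this is a pilot study".

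The analysis plan is one short paragraph just before the references. It contains:

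- a significance rule: "A two-tailed PValue less than 0.05 will be considered as statistical significance in this study";
- descriptive statistics, namely frequency distributions, means with SD, and "95% confidence intervals, to be calculated for demographic and treatment variables";
- the group comparison, by "One way ANOVA or Krsukal Wallis test and categorical comparison will be done using Chi Square test".

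Elsewhere in Material and methods a mean cavity visualisation score is planned for each group. The plan contains no pairwise contrast, no between-group effect estimate, no interval for a difference, no equivalence margin, and no rule for interpreting a non-significant result.

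**The concern.** The objective is comparative, but the only comparative output is an omnibus p-value. A three-group ANOVA or Kruskal-Wallis test asks whether the groups are all alike. It does not say which technique stands apart or how far. The planned intervals do not fill the gap: they are descriptive, and an interval for one group's mean is not an interval for the difference between two groups.

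This matters more in a small pilot than in a large trial. What a pilot can usefully hand on is the estimated size of the differences, their uncertainty, and the SDs needed to plan a later study. With 20 patients, p>0.05 is a likely result even if the techniques differ substantially, and the p-value alone does not tell the reader so.

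The background section shows how such a result can be phrased. It cites a closure-technique series of 29 versus 16 patients that "did not find statistically significant difference in mean cavity visualization scoring", although 79% versus 63% had a score above 2. The title of that article, in the reference list, words the finding as closure technique having no effect on dosimetry. The present study has 20 patients in three groups, against 45 in two.

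**Working it through.** **Inputs from the document.** N = 20, three groups, two-tailed alpha 0.05. The document gives no power, effect size or SD, so the figure of 20 cannot be reproduced; it is stated as an uncalculated pilot number.

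**Assumptions.** Common SD in the three groups and approximately normal outcomes. Group sizes are not given. I use 7/7/6 as the near-balanced case, and 10/6/4 and 12/5/3 as a range, since the groups are formed by the surgery patients happened to have.

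**Step 1: precision of a pairwise difference.**

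Half-width in SD units = t(0.975, 17) × √(1/n₁ + 1/n₂), with df = 20 − 3 = 17 and t = 2.110.

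- 7 vs 7: 2.110 × √(1/7 + 1/7) = 2.110 × 0.5345 = 1.13
- 7 vs 6: 2.110 × √(1/7 + 1/6) = 2.110 × 0.5563 = 1.17

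For Tukey simultaneous intervals, replace t by q(0.95; 3, 17)/√2 = 3.628/√2 = 2.565. This gives 1.37 (7 vs 7) and 1.43 (7 vs 6).

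| Split | Unadjusted half-width (SD) | Tukey half-width (SD) |
|---|---|---|
| 7/7/6 | 1.13 to 1.17 | 1.37 to 1.43 |
| 10/6/4 | 1.09 to 1.36 | 1.32 to 1.66 |
| 12/5/3 | 1.12 to 1.54 | 1.37 to 1.87 |

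An observed difference of exactly zero would therefore still be compatible with a true difference of more than 1 SD in either direction.

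**Step 2: what the omnibus test can detect.**

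Power = P[F′(2, 17, λ) > F(0.95; 2, 17)], with critical value 3.59 and λ = Σ nᵢ(μᵢ − μ̄)²/SD², which equals N f² for Cohen's f.

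- f = 0.40: λ = 20 × 0.16 = 3.2, power 29%.
- 80% power needs f = 0.76 (λ = 20 × 0.76² = 11.6).
- True range of 1 SD at 7/7/6: power 37% if only the group of 6 is shifted, 29% if the three means are evenly spaced.
- The same two patterns give 29% and 28% at 10/6/4, and 24% and 25% at 12/5/3 (the smallest group being the one shifted).

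A true 1 SD range would thus give p>0.05 in about 63% to 76% of such studies.

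**Step 3: the cited series as an illustration.** The percentages 79% of 29 and 63% of 16 imply 23/29 and 10/16 (counts inferred). The difference is 0.793 − 0.625 = 0.168, about 17 points, with a Newcombe 95% CI of about −9 to +43 points. Non-significance there is consistent with no difference and also with a large one. An interval makes that visible.

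**The case against.** Five arguments can be made for the plan as it stands.

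1. **The protocol never says it will treat p>0.05 as no difference.** A reader might infer that a null result will be reported as technique making no difference. The document does not support that: there is no equivalence hypothesis, margin or interpretation rule. The background handles the earlier null result with care, giving the 79% versus 63% contrast and naming small numbers as a limitation. The no-effect wording belongs to the cited article's title, not to this protocol. The misreading is a credible risk and no more. This objection stands.

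2. **Treatment variables is undefined and may include dosimetry.** A reader might infer that the main endpoints get no interval at all; that cannot be shown. If dosimetry is covered and summaries are given by group with n, a reader could derive an approximate interval for a mean difference. This stands as a limit on the claim. It does not supply a planned estimate of any difference.

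3. **Low power comes from N = 20, which the protocol openly calls a pilot number.** Correct. Changing the analysis does not change power. Step 2 shows only why the p-value alone is weak evidence here; the half-widths in Step 1 are the figures that bear on this point.

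4. **An omnibus test is a valid three-group analysis, and nothing forbids follow-up contrasts.** Also correct. The gap is that none is planned.

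5. **Pairwise intervals have costs.** They do. Three unadjusted 95% intervals have joint coverage of about 88% (balanced groups, df 17). The protocol names no lead variable. It lists three volume measures, plus RCI, DHI and five normal structures under two plans each: 3 + 7 × 2 = 17 measures at least, or 17 × 3 = 51 pairwise intervals. Ratios of geometric means would also break down for seroma cavity volume, because the scoring scale allows no visible seroma and the background says seroma does not develop after closed-cavity surgery. The remedy has to deal with each of these.

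**Conclusion.** The gap is real. The plan provides no effect estimate or confidence interval for any between-technique difference, and its group comparison is an omnibus test that identifies neither which technique differs nor by how much. The data remain valid and the test is legitimate; what is limited is what can be concluded about the primary objective.

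The size of the issue is the uncertainty left undisplayed. Over the three assumed splits, unadjusted half-widths run from 1.09 to 1.54 SD and Tukey half-widths from 1.32 to 1.87 SD. These figures depend on the assumed group sizes and a common SD, neither of which the document gives. The document does not address dropout; any loss would widen the intervals. This is a worthwhile, inexpensive improvement, not a fatal flaw.

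**What to change.** Amend the statistical paragraph as follows.

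- For the dosimetric variables already listed in Material and methods, report each pairwise difference (closed versus open, oncoplasty versus open, oncoplasty versus closed) with a 95% CI. Use the mean difference, or the Hodges-Lehmann shift where Kruskal-Wallis is used. Use the shift for seroma cavity volume too, where zeros are possible.
- Either use Tukey-type simultaneous intervals or label the intervals as unadjusted and exploratory.
- Keep the omnibus p-value as supportive.
- State that p>0.05 will not be interpreted as absence of a difference.

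This needs a few sentences of wording and somewhat more analysis on the same data, with no extra patients and no change to treatment. The downside is a large set of wide intervals across many measures, which must be presented as exploratory. Power is unchanged.

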Informed consent will be taken for all patients at the time of Radiotherapy simulation. All patients will first receive external beam Radiotherapy to the whole breast to a dose of 40Gy/15#/3weeks. The patients will then be planned for boost radiation to the tumor bed to a dose of 12.5 Gy/5#.

The combination of surgical clips with a treatment planning CT scan for the lumpectomy site for electron boost and to determine the appropriate energy will be used for tumour bed boost delineation

For the boost planning CT scan a small thermocol wedge will be used, with a pillow under the shoulder to make the surface as flat as possible.

The pT size in HPR of lumpectomy plus a margin of 2 cm in all directions is the approximate size of the boost field. The margins of this field are marked on the skin with the centre of scar as the center of the field and copper wire is placed on the markings.

5 mm slice thickness CT scan will be taken in the treatment position. After the scan acquisition the data will be transferred to the Varian Eclipse treatment planning system.

The post-operative cavity depicted on the CT images will be contoured section by section. All available images will be assigned a cavity visualisation score⁹ (CVS) as per the British Columbia Cancer Agency Cavity visualisation score 0-No visible seroma, 1-scar/shadow, 2-seroma identifiable but with significant (>30%) uncertainties, 3-seroma identifiable with minor (<30%) uncertainties, 4- seroma easily identifiable, generally homogenous with some blurring of margin, 5-seroma clearly identifiable, homogenous with sharp boundaries. The mean cavity visualisation score will be determined for each group of patients.

The CTV will be generated by using a 15 mm uniform expansion from the lumpectomy cavity but limited by skin and chest wall. The CTV will be extended by an additional 10 mm uniform expansion to generate the PTV

Treatment plans for tumor bed boost irradiation will be made using both electrons and photons with 3DCRT technique for each patient and comparison will be made for various dosimetric variables. The photon beam plan will only be generated for purposes of dosimetric study and will not be used for treatment of the patients

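### Electron and photon plans for the same patient are to be compared, but the plan names no paired method; its only tests for continuous data are for independent groups and are tied to no comparison.

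*Combined protocol and SAP*

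**What the plan says.** The primary objective, under Aims and Objectives, concerns surgical technique: "To evaluate dosimetric outcomes in tumor bed boost irradiation in patients undergoing breast conservative surgery using three different surgical techniques". Under Material and methods, 20 patients are divided into three groups (open cavity, closed cavity, oncoplasty), and no sample size was calculated because the study is a pilot.

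The same section adds a second, within-patient contrast. Boost plans are prepared with electrons and with photons "for each patient and comparison will be made for various dosimetric variables". The photon plan is never delivered: "The photon beam plan will only be generated for purposes of dosimetric study". The paragraph on dosimetric variables then measures both plans: "The Radiation Conformity Index (RCI) will be determined for both set of plans". The dose homogeneity index (DHI) is treated in the same way, and so are the organ doses: "The dose received by several normal structures will be determined for both set of plans".

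The closing statistical paragraph of the section has three relevant statements:

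- the significance rule: "A two-tailed PValue less than 0.05 will be considered as statistical significance in this study";
- the descriptive statistics, which include "95% confidence intervals, to be calculated for demographic and treatment variables";
- the tests: "The statistical analysis will be carried out using the One way ANOVA or Krsukal Wallis test", with chi-square for categorical comparisons.

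The document names no paired t-test, signed-rank test, repeated-measures analysis or mixed model.

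**The concern.** An electron plan and a photon plan for one patient share the same CT scan, target volume and anatomy, so their RCI, DHI and organ doses will tend to rise and fall together. The information about the difference between plan types lies in the within-patient differences. One-way ANOVA and Kruskal-Wallis treat the two sets of 20 values as 40 unrelated patients.

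The test sentence is worded as covering the statistical analysis as a whole and is not limited to the surgical groups. An analyst who follows it literally has only independent-group tests for the electron-photon comparison. An analyst who assigns those tests to the surgical groups has no method for it and must choose one after seeing the data.

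With positive correlation, the ANOVA applied to paired data is conservative. The interval for the difference is too wide, and a modest difference between modalities can be missed. The promised confidence intervals do not repair this, because intervals for each treatment variable are not an interval for the within-patient difference.

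**Working it through.** There is no stated figure to reproduce, since the sample size was set without a calculation. The check sizes what would happen if the named tests were used for electron versus photon.

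**Inputs from the protocol.** 20 patients, hence 20 pairs; two-sided alpha 0.05.

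**Inputs assumed, because the documents give none.** Normal data; within-patient correlation ρ of 0, 0.3, 0.5 and 0.7; SD ratio k between plan types of 1, 2 and 4; true difference of 0, 0.5 or 1.0, in units of the root-mean-square SD of the two plan types.

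**Standard errors.** With SDs σ₁ and σ₂ and σ₁² + σ₂² = 2 (root-mean-square SD of 1), the unpaired analysis uses SE = √(2/20). The correct SE is √[(2 − 2ρσ₁σ₂)/20]. With k = σ₁/σ₂, the ratio of unpaired to paired SE is

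1/√[1 − ρ·2k/(1 + k²)].

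For k = 1 this is 1/√(1 − ρ): 1/√0.7 = 1.20, 1/√0.5 = 1.41 and 1/√0.3 = 1.83. For k = 2 the factor 2k/(1 + k²) is 4/5 = 0.8; at ρ = 0.5 the ratio is 1/√(1 − 0.4) = 1.29. For k = 4 the factor is 8/17 = 0.47; at ρ = 0.5 the ratio is 1/√(1 − 0.235) = 1.14.

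**Power of the paired t-test.** This is the noncentral t with 19 degrees of freedom and noncentrality 0.5·√[20/(2 − 2ρσ₁σ₂)]. For k = 1 and ρ = 0.5 the variance of a difference is 2 − 1 = 1, the noncentrality is 0.5·√20 = 2.24, and power is 56%.

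**Power and type I error of the unpaired test.** These were obtained by simulating correlated pairs and applying the two-group t-test, which is identical to a two-group one-way ANOVA.

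| SD ratio | ρ | SE ratio | Power at 0.5 SD, unpaired vs paired | Unpaired type I error (nominal 5%) |
|---|---|---|---|---|
| 1 | 0.3 | 1.20 | 31 vs 43% | 2.1% |
| 1 | 0.5 | 1.41 | 29 vs 56% | 0.7% |
| 1 | 0.7 | 1.83 | 25 vs 78% | 0.1% |
| 2 | 0.3 | 1.15 | 32 vs 41% | 2.8% |
| 2 | 0.5 | 1.29 | 31 vs 49% | 1.5% |
| 2 | 0.7 | 1.51 | 28 vs 62% | 0.6% |
| 4 | 0.3 | 1.08 | 33 vs 37% | 4.0% |
| 4 | 0.5 | 1.14 | 33 vs 40% | 3.1% |
| 4 | 0.7 | 1.22 | 32 vs 45% | 2.2% |

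Repeat simulations agree within about one percentage point.

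**Limits of the effect.** At ρ = 0 with equal SDs there is no loss: 34% unpaired against 32% paired. At a true difference of 1.0 SD, the unpaired t-test already has 88 to 97% power over the cells in the table, and about 87% at ρ = 0. Large differences would therefore usually be found either way.

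**Rank tests.** At 0.5 SD, Kruskal-Wallis against Wilcoxon signed-rank gives 30 vs 42%, 27 vs 54% and 23 vs 76% for equal SDs at ρ = 0.3, 0.5 and 0.7. At SD ratio 4 it gives 33 vs 36%, 33 vs 39% and 31 vs 43%. Kruskal-Wallis is not always conservative: at SD ratio 4 and ρ = 0.3 its type I error is 5.9%.

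**The case against.** The strongest reply is that this is an omission and not a wrong test. The plan never says that ANOVA or Kruskal-Wallis will be applied to electron versus photon. Both fit the three surgical groups, and that is their most natural use. The power figures then describe a misuse that the plan does not announce. This stands, so the harm is stated here as conditional. But on this reading a comparison to which the protocol commits has no method at all.

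A second reply is that the modality comparison may be descriptive only. It is not a listed objective, and every patient is boosted with electrons whatever the result. That reading is possible, but the significance rule is set for the whole study and does not exempt this comparison. A descriptive report would still need an interval for the within-patient difference, which the plan does not provide.

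A third reply is that the consequence is small: the ANOVA error is mainly in the conservative direction, the study is a pilot with no power claim, and the correlation and SDs are assumed. All of this stands and limits the weight of the point. It does not remove the gap, because the paired analysis uses data already collected and costs nothing more.

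**Conclusion.** The concern holds, with high confidence as to the gap itself. The plan commits to comparing two plans made for the same patient, names no paired method, and leaves its only tests for continuous data, both for independent groups, unassigned.

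The size of the consequence is uncertain. It depends on a within-patient correlation, SD ratio and effect size that the documents do not give, and on normality. Over the assumed range it runs from no loss at zero correlation to a fall from 78 to 25% power at 0.5 SD with correlation 0.7 and equal SDs. The practical weight is modest, given the pilot status and the absence of this comparison from the objectives. The three-group comparison in the primary objective is unaffected as long as it uses one value per patient. The point should be fixed, but it does not threaten the study.

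**What to change.** Add two sentences to the statistical paragraph of Material and methods:

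1. Electron versus photon: RCI, DHI and each normal-structure dose will be compared by a paired t-test or Wilcoxon signed-rank test on the within-patient differences, and the difference will be reported with its 95% confidence interval.
2. Surgical technique: the three groups will be compared by one-way ANOVA or Kruskal-Wallis separately within each plan type, with one value per patient.

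It would help to state at the same time how the choice between the parametric and the rank test is made, to name an interval that matches the signed-rank test (for example Hodges-Lehmann), and to say whether the modality comparison is exploratory.

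The cost is a small wording change. Both values already exist for each patient, so no data collection, treatment or sample size changes.

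### The chi-square test is named for categorical data with no exact alternative, yet with 20 patients no three-group table can meet its usual expected-count condition, and it would ignore grade order if applied to cosmesis

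*Combined protocol and SAP*

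**What the plan says.** All of this stands in the unnumbered *Material and methods* section of the combined protocol and SAP.

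- **Size.** "Twenty patients will be accrued for the purpose of this study", and "The sample size has not been calculated as this is a pilot study".
- **Groups.** "The patients will be divided into three groups" according to the surgery already done (for example, "Group A- Patients who underwent open cavity BCS"). No number per group is set.
- **Cosmesis.** It is graded before radiotherapy, at its end and 6 months later, on four ordered grades from excellent to poor; the third reads "Fair: obvious difference between the two sides without major distortion".
- **Tests.** "The statistical analysis will be carried out using the One way ANOVA or Krsukal Wallis test", and in the same sentence "categorical comparison will be done using Chi Square test". No test is tied to a named variable. No exact test or rule for sparse tables is given.
- **Threshold.** "A two-tailed PValue less than 0.05 will be considered as statistical significance in this study".

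**The concern.** The chi-square p-value is a large-sample approximation, and the customary check on it is that at least 80% of expected counts are 5 or more. Twenty patients spread over three groups are too few for that. The plan nevertheless sets a 0.05 threshold and gives the analyst nothing else to use for categorical data. A table with one or two rare events could be declared significant when an exact calculation says otherwise.

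A second issue is conditional. The chi-square statistic does not change if the columns are shuffled, so it discards the order of the cosmesis grades. If cosmesis is compared between techniques in this way, a consistent shift towards better or worse grades is more easily missed than with a rank test. Cosmesis is the secondary objective and the only clinical outcome in the study.

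**Working it through.** **Inputs.** From the protocol: N = 20, three groups, four cosmesis grades, two-sided 0.05. The plan has no sample-size calculation to reproduce. Group sizes and grade frequencies are not given, so every simulated figure below rests on stated assumptions. Step 1 needs none.

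**1. Expected counts.** Expected counts sum to N, so at most 20/5 = 4 cells can reach 5. A table with three rows and C columns needs at least 0.8 x 3C cells at 5 or more, rounded up.

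- 3x2: 0.8 x 6 = 4.8, so 5 cells, and N must be at least 5 x 5 = 25.
- 3x4: 0.8 x 12 = 9.6, so 10 cells, and N must be at least 10 x 5 = 50.

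Enumerating every split of 20 and every set of column totals shows that at best 50% of cells reach 5 in a 3x2 table and 25% in a 3x4 table. The average expected count is 20/6 = 3.33 and 20/12 = 1.67.

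**2. Single tables.** Suppose one event occurs among 20 patients, in the smallest group, of size n. Then chi-square = ((20 - n)/n) x (20/19) on 2 df, and the upper tail is exp(-chi-square/2). The exact p is n/20, the chance that the one event falls in that group.

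| n | chi-square | chi-square p | exact p |
|---|---|---|---|
| 2 | 9 x 20/19 = 9.47 | 0.009 | 0.10 |
| 3 | 5.667 x 20/19 = 5.96 | 0.051 | 0.15 |

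A second example has rows (12,2,0), (3,1,0), (1,0,1). It gives chi-square p = 0.043 against a permutation p of 0.128.

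**3. Overall type I error.** Simulated rejection rates at nominal 0.05 for 3x4 tables (200,000 runs each). The range is over five assumed grade mixes: 35/40/20/5, 60/30/8/2, equal, 20/60/15/5 and 80/15/4/1%.

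| Assumed groups | Chi-square | Kruskal-Wallis |
|---|---|---|
| 7/7/6 | 0.020-0.040 | 0.036-0.044 |
| 10/6/4 | 0.026-0.040 | 0.030-0.044 |
| 12/5/3 | 0.038-0.042 | 0.038-0.040 |
| 14/4/2 | 0.042-0.091 | 0.030-0.046 |

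**4. Power if cosmesis is compared between groups.** Assumed grade mix 20/40/30/10%, groups 7/7/6, and one group shifted by a common cumulative odds ratio. The ranges are approximate, because the result depends on which group shifts and in which direction, and carries simulation error.

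| Odds ratio | Chi-square | Kruskal-Wallis |
|---|---|---|
| 3 | 8-9% | 13-15% |
| 5 | 16-18% | 27-30% |
| 10 | 29-35% | 50-56% |

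Under a different assumption, a graded shift over all three groups with log odds ratio 1.5 per step, the figures are 34-43% against 59-65% at 7/7/6, and 41-48% against 55-62% at 10/6/4. At 14/4/2 the advantage of Kruskal-Wallis for a shift in one group largely vanishes or reverses; chi-square's own error rate there is near or above nominal.

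As an illustration, rows (4,3,0,0), (1,4,2,0), (0,2,3,1) show a clear ordered trend. Chi-square gives p = 0.096 (permutation 0.069) and Kruskal-Wallis p = 0.012 (permutation 0.005).

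The Kruskal-Wallis rates in steps 3 and 4 use its usual large-sample p-value. The exact version was not simulated.

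**The case against.** Four objections have weight.

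*The plan does not assign chi-square to cosmesis.* A reader might infer that it fixes this test for comparing grades between techniques. The documents do not support that. No variable is mapped to a test, Kruskal-Wallis is named in the same sentence, and the grades are numbered 1 to 4, so a rank analysis would be consistent with the text. The secondary objective speaks of evaluating cosmesis at three times; only the primary, dosimetric objective mentions the surgical techniques. A between-group comparison of cosmesis is therefore itself an inference. This stands, and it makes the power loss conditional. It does not touch step 1, which applies to any three-group categorical table.

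*Error control mostly holds.* A reader might also infer that chi-square will generally produce too many false positives. Step 3 shows otherwise: the rate stays at or below about 4% for the three less extreme splits and is inflated only at 14/4/2. The group-of-3 example, at 0.051, does not even cross the threshold. This stands too. What remains is that a single sparse table can mislead, and very uneven groups cannot be ruled out because past surgery determines them.

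*The power gain matters little at moderate effects.* At odds ratio 3 both tests would usually miss the difference. That is correct: the better test does not rescue a sample of 20.

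*It is a pilot.* The plan still sets a significance threshold and names tests, and a small sample is the setting in which large-sample p-values are least reliable.

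**Conclusion.** The point holds within limits. The arithmetic is certain: with 20 patients, no three-group table can satisfy the usual expected-count condition, and the plan offers no exact alternative. The consequence is that individual p-values can be wrong, sometimes by a factor of about ten (0.009 against 0.10). It is not a general excess of false positives.

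The loss from ignoring grade order follows only if cosmesis is compared between groups as a categorical variable. On that reading it costs about 4 to 7 percentage points of power at odds ratio 3 and about 15 to 27 at odds ratio 10 (the extremes of the ranges in step 4), under an assumed grade mix and near-equal groups. The advantage of a rank test is not assured with very uneven groups.

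The primary dosimetric outcomes are continuous and are not affected. The matter concerns secondary and descriptive categorical variables, and is worth correcting because the correction is so small.

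**What to change.** Replace the chi-square clause in the statistical paragraph with:

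> Unordered categorical variables will be compared between groups by the Fisher-Freeman-Halton exact test. Any between-group comparison of cosmesis grades at a visit will use the Kruskal-Wallis test with exact or Monte Carlo p-values.

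This also settles which test applies to the grades. Exact or Monte Carlo p-values are advisable for Kruskal-Wallis too, because its large-sample p-value is itself approximate at this size. The cost is this change to the paragraph and the exact-test option in the named package, or free software. No further patients or data are needed.
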